- 3. Severe other diseases which started before the "study pregnancy" and lasted into the "study pregnancy" period, including congenital heart disease, arrhythmia, history of myocardial infarction (MI), history of stroke, or active cancer
- 4. Serious physical injury that occurred during the "study pregnancy": severe car collision injury, serious injury at home/work, etc. Multiple gestation (i.e., pregnancy with more than one baby at a time, such as pregnancy with twins, triplets, and quadruplets) in the "study pregnancy"

Study Design and Recruitment

Study group: Study group participants will be recruited from Nerivio's user base. An invitation message will be sent via in-app notification and/or email to all Nerivio users who are (1) female, AND (2) between 18 and 42 years of age as of November 1st, 2019 - March 31st, 2021. Users who meet these criteria will be invited to fill in a screening and eligibility questionnaire. If they meet the eligibility criteria, they will be offered the opportunity to participate in the study. Participants will complete and sign an electronic informed consent form. Following consent, participants will be asked to complete the questionnaire. Once complete, participants will be compensated for their time.

Control group: Control group participants will be referred to the study by site co-investigators, who are US licensed healthcare providers seeing women with headache disorders and/or women during their pre-pregnancy and/or pregnancy period. Patients interested in participating will be directed to the same screening and eligibility questionnaire and will follow the same study design.

Endpoints

Endpoints focus on the health of the mother and the baby, during pregnancy and three months postpartum.

Primary endpoint:

Demonstrate that the study group is not different than the control group in regard to gestational age at delivery (measured in pregnancy weeks).

QMS document

TCH-011 Clinical Study Protocol

Doc ID: TECXXXX

Revision #: 1.0

Page: 6 of 25

Secondary endpoints:

Demonstrate that the study group is not different from the control group in:

- 1. Baby's birth weight (average birth weight)
- 2. Miscarriage rate (% of miscarriage cases)
- 3. Preterm birth rate (% cases of preterm pregnancies, as measured in % of pregnancy weeks less than 37)
- 4. Birth deficits rate (% of birth deficits)
- 5. Still births rate (% of still births)

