- 6. Meeting developmental milestones following 3 months postnatal (% of babies)
- 7. Visits to the emergency room or urgent care due to pregnancy and/or migraine symptoms during pregnancy and 3 months postpartum period (# of events)

Exploratory endpoints: Difference between the study group and the control group in:

- 1. Overall subjective **feeling of safety** using acute migraine treatments during pregnancy (in subjects who used such treatments).
- 2. Overall subjective **satisfaction** with the acute migraine therapies used during the pregnancy (in subjects who used such treatments).
- 3. APGAR score at 5 minutes.

Data analysis

Statistical Hypothesis

The goal of the proposed study is to test the null hypothesis that treating with Nerivio during pregnancy does not impose a safety risk relative to standard care migraine treatment for pregnant women. In other words, the hypothesis is that the means of the two populations are equal. Thus, in this study, the following hypotheses will be tested:

• Null hypothesis: H0: GAt = GAc

• Alternate hypothesis: H1: GAt ≠ GAc

Where GAt and GAc are the average Gestational Age in the study group and control group, respectively. If the null hypothesis is not rejected, the study will be deemed successful. The criterion for significance has been set at 0.05. The test is 2-tailed.

TCH-011 Clinical Study Protocol

Doc ID: TECXXXX

Revision #: 1.0

Page: 7 of 25

Planned Sample Size

Based on USA data from 2020 [Osterman M, et al. Births: Final Data for 2020. Natl Vital Stat Rep. 2021] we assume mean gestational age (GA) of 38.4 with standard deviation of 2.7 (range 26-42).

With the proposed sample size of 114 for each group, the study will have power of 80% to yield a statistically significant result. This computation assumes that the mean difference is less than 1.0 week, and the common within-group standard deviation is 2.7. This effect was selected as the smallest effect that would be important to detect.

Precision for estimating the effect size: We further estimate the mean difference between the two populations. On average, a study of this design would enable us to report the mean difference with a precision (95% confidence level) of plus/minus 0.70 weeks.

Given this statistical requirement up to 400 participants will be recruited per group.

Statistical Analysis Plan

Data will be collected from all patients recruited to the study. Data analysis will not include patients who are:

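### The success verdict on safety rests on mean gestational age alone, so a significant excess of birth defects (and, on one reading, of fetal losses) could not block it

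*Combined protocol and SAP*

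**What the plan says.** The Statistical Hypothesis section sets the study's aim in these words: "test the null hypothesis that treating with Nerivio during pregnancy does not impose a safety risk relative to standard care migraine treatment for pregnant women". The next sentence narrows this to one parameter: "In other words, the hypothesis is that the means of the two populations are equal". The formal statement is "Null hypothesis: H0: GAt = GAc", and the symbols are defined so that only average gestational age is involved: "Where GAt and GAc are the average Gestational Age in the study group and control group, respectively". The test is two-sided at 0.05, and the decision rule is "If the null hypothesis is not rejected, the study will be deemed successful". The documents contain no other success rule.

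Under Endpoints, the primary endpoint is gestational age at delivery. Miscarriage, preterm birth, birth defects and stillbirth appear among seven secondary endpoints, introduced by "Demonstrate that the study group is not different from the control group in". No test, margin, significance level or consequence for the verdict is given for any of them. The section headed Statistical Analysis Plan lists only exclusions from the analysis: BMI, date of last menstrual period, too little Nerivio use in the study group, and any Nerivio use in the control group.

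**The concern.** A primary endpoint normally supports a claim about that endpoint. This plan goes further: it makes one mean stand for the whole question of safety in pregnancy, and no other result can alter or qualify the verdict.

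Mean gestational age carries no information about a malformation in a pregnancy that runs to term. It also carries none about a pregnancy loss that is left out of the mean. The study could therefore be called successful on its stated safety hypothesis while its own data show a significant excess of an outcome it set out to examine. Replacing the equality test with a non-inferiority or equivalence test on gestational age would not close this gap, because such a test looks at the same mean.

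**Working it through.** **1. The plan's own figure.** Planned Sample Size gives a difference of 1.0 week, SD 2.7, two-sided 0.05 and 80% power.

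- n per group = 2 × [(1.960 + 0.842) × 2.7 / 1.0]² = 114.4. The plan states 114, where power is 79.8%.
- Precision = 1.96 × 2.7 × √(2/114) = 0.70 weeks, as stated.

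The design figures reproduce, and all of them concern gestational age. The documents give no event rate for any secondary outcome, so every rate below is an assumption.

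**2. Chance of success when mean gestational age is equal.** This is 1 − 0.05 = 0.95 at any sample size. An outcome that leaves gestational age unchanged does not enter the calculation.

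**3. Birth defects that do not shorten pregnancy.** Assumed counts, with 114 as denominator in each group: control 3 (2.6%), Nerivio 11 (9.6%).

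- Fisher exact two-sided p = 0.0499. Eleven is the smallest count that reaches 0.05 against 3.
- Risk difference = 0.0965 − 0.0263 = 0.0702.
- SE = √(0.0263 × 0.9737/114 + 0.0965 × 0.9035/114) = 0.0315.
- 95% CI = 0.0702 ± 1.96 × 0.0315, or 0.9 to 13.2 percentage points.

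The chance that a study is both successful under the rule and shows a significant defect excess is 0.95 × power for the defect comparison. The plan allows recruitment of up to 400 per group, so both sizes are shown.

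| Assumed true defect rates | 114 per group | 400 per group |
|---|---|---|
| 3% vs 9% | 0.95 × 0.479 = 45% | 0.95 × 0.948 = 90% |
| 3% vs 6% | 0.95 × 0.192 = 18% | 0.95 × 0.535 = 51% |

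A larger study makes the contradiction more likely.

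**4. Pregnancy losses.** The documents point two ways. The primary endpoint is measured at delivery and the planning range is 26–42 weeks, which suggests births only. Question 20 of the survey asks for gestational age at delivery or at the end of pregnancy and accepts 6 to 42 weeks, and losses are not among the listed exclusions. Both readings were simulated (4,000 runs each), with births at mean 38.4 and SD 2.7 in both groups. Kept miscarriages were placed uniformly at an assumed 6–20 weeks and kept stillbirths at an assumed 20–40 weeks. Each cell gives the chance of success, then the chance of success together with a significant excess of losses.

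| Assumed loss rates and reading | 114 per group | 400 per group |
|---|---|---|
| Miscarriage 5% vs 15%, births only | 95%; 71% | 95%; 95% |
| Miscarriage 5% vs 15%, losses in the mean | 33%; 10% | 0.5%; 0.4% |
| Miscarriage 10% vs 20%, births only | 94%; 53% | 95%; 93% |
| Miscarriage 10% vs 20%, losses in the mean | 48%; 8% | 3%; 2% |
| Stillbirth 1% vs 5%, kept in the mean | 88%; 33% | 68%; 62% |
| Stillbirth 0.6% vs 3%, kept in the mean | 93%; 21% | 85%; 61% |

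For miscarriage, the reading decides whether the rule is blind. Stillbirths move the mean only modestly even when they are kept in it.

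**5. What a harm check can and cannot do.** Four checks, each one-sided at 2.5%, raise a false alarm in at most 4 × 2.5% = 10% of studies with no harm (1 − 0.975⁴ = 9.6% if independent). A 95% Wald interval for the risk difference fails to exclude 0 for an assumed doubling of defects (3% to 6%) about 82% of the time at 114 per group and 46% at 400. For an assumed doubling of stillbirth (0.6% to 1.2%) the figures are about 97.5% and 87%.

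**The case against.** **One primary endpoint is ordinary practice.** The other outcomes are pre-specified and would be reported, and the rule calls the study successful, not the device safe. This is fair as far as it goes. A reader might infer that the plan ignores the secondary outcomes or declares the device safe in so many words, and the documents support neither. What remains is that the hypothesis being judged is itself worded as absence of a safety risk, and nothing lets a secondary result qualify the judgement.

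**Losses may be visible to the test.** A reader might infer that mean gestational age cannot register miscarriages at all. The documents do not support that. The 26–42 week range is a sample-size assumption and does not define the analysis set, and question 20 gives losses a value. With losses at an assumed 6–20 weeks kept in the mean, assumed true rates of 10% vs 25% at 114 per group leave success at only about 17%. With counts fixed at 11 vs 28 it is about 0.1%. This objection stands, and the point about losses is conditional on the reading.

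**The sizes are chosen.** This also stands. The 3 versus 11 example sits just below 0.05 and is an illustration, not a forecast. The 95% figure, however, depends on none of these rates.

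**Preterm birth is not hidden from the mean.** This is correct, because it is defined from gestational age. It still has no part in the decision rule.

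**The worse fault is treating non-rejection as success.** That is a separate matter, and correcting it would leave this one in place.

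**Conclusion.** The point holds. Success on a broadly worded safety hypothesis is decided by mean gestational age alone. For birth defects that do not shorten pregnancy this is so on every reading of the documents: with equal mean gestational age the verdict is success about 95% of the time, whatever the defect rate. For miscarriage and stillbirth it holds fully only if the mean is taken over births in which those losses do not appear, and the plan does not settle this.

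The 95% rests only on the stated two-sided 0.05 level and equal mean gestational age. How often success would coincide with a significant excess of harm rests on assumed rates: for defects, 18% to 45% of studies at 114 per group and 51% to 90% at 400.

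A reader might also infer that adding a check for significant harm would justify a conclusion of no risk. It would not. At these sample sizes such a check misses most doublings of a rare outcome, so it can block a verdict but cannot establish safety.

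**What to change.** Replace the success sentence in the Statistical Hypothesis section with three statements:

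1. Meeting the gestational-age criterion supports a conclusion about length of gestation only.
2. No overall statement of success or safety is made if the 95% CI for the risk difference in miscarriage, preterm birth, birth defects or stillbirth excludes 0 towards harm.
3. Absence of such a signal is not evidence of no risk. Each rate difference is reported with its 95% CI and a statement of the excess that the interval cannot rule out.

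The plan should also say whether pregnancies ending in loss enter the gestational-age mean. That settles how far the rule can see losses, but it does not replace the three statements, because birth defects stay outside the mean either way.

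The cost is one paragraph of wording and no new data, since the outcomes are already planned. The downsides are a false-alarm chance of up to about 10% from the four checks and a narrower headline conclusion.

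### The 80% power statement gives its condition in the wrong direction: 114 per group has 80% power at a difference of about 1.0 week or more, not below 1.0 week

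*Combined protocol and SAP*

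**What the plan says.** All the relevant text is under Data analysis in the combined protocol and SAP.

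- **Statistical Hypothesis.** The primary comparison is a test of difference in mean gestational age at delivery: "Alternate hypothesis: H1: GAt ≠ GAc". The error rate is fixed by "The criterion for significance has been set at 0.05" and "The test is 2-tailed". The success rule is "If the null hypothesis is not rejected, the study will be deemed successful".
- **Planned Sample Size, power.** "With the proposed sample size of 114 for each group, the study will have power of 80% to yield a statistically significant result". The next sentence gives the condition: "This computation assumes that the mean difference is less than 1.0 week", with a common within-group standard deviation of 2.7 weeks. The sentence after that describes the effect as the smallest one worth detecting.
- **Planned Sample Size, precision and recruitment.** The expected 95% precision of the mean difference is plus or minus 0.70 week. Recruitment may go up to 400 per group.

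No equivalence or non-inferiority margin is stated in either section.

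**The concern.** Power to reject equality of two means rises with the true difference. A statement that a design has 80% power therefore needs a floor (this difference or larger). The plan gives a ceiling (smaller than this difference). Taken as written, it says the design would reach significance 80% of the time for true differences under 1.0 week, which includes differences close to zero, where power is close to the 5% significance level.

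In many trials this would be a slip of little consequence. Here success is a non-significant result, so the power statement is the part of the plan that tells a reader which differences such a result could have missed. If its condition is reversed, the reader is told that the design is sensitive in the range where it is not.

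**Working it through.** **Inputs, all from the Statistical Hypothesis and Planned Sample Size sections:** two-sided alpha 0.05; 114 per group, equal groups; standard deviation 2.7 weeks; stated power 80%; reference difference 1.0 week; stated precision 0.70 week; recruitment ceiling 400 per group.

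**Step 1. Reproduce the plan's figures at exactly 1.0 week.**

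Standard error of the difference: 2.7 × √(2/114) = 0.3576 week.

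Precision: 1.96 × 0.3576 = 0.70 week. This matches the plan.

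Sample size per group: 2 × (1.96 + 0.8416)² × 2.7² / 1.0² = 114.4, which rounds up to 115. The stated 114 is within rounding.

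Power at 1.0 week: Φ(1.0/0.3576 − 1.96) = Φ(0.836) = 79.8%. The noncentral t distribution with 226 degrees of freedom gives 79.5%. This matches the stated 80%.

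**Step 2. Find where 80% power begins.** Solving for the difference that gives 80% power at 114 per group yields 1.002 weeks (normal approximation) or 1.006 weeks (noncentral t). So 80% is reached at about 1.0 week and above, and at no smaller difference.

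**Step 3. Compute power on both sides of 1.0 week.** The normal approximation is Φ(d/0.3576 − 1.96), where d is the true difference. It leaves out the far tail, which is negligible at 0.5 week and above.

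| True difference (weeks) | 114 per group, normal | 114 per group, noncentral t | 400 per group, noncentral t |
|---|---|---|---|
| 1.1 | 86.8% | 86.5% | >99.9% |
| 1.0 | 79.8% | 79.5% | 99.9% |
| 0.9 | 71.1% | 70.7% | 99.7% |
| 0.8 | 60.9% | 60.5% | 98.7% |
| 0.75 | 55.5% | 55.1% | 97.5% |
| 0.5 | 28.7% | 28.5% | 74.4% |
| 0.25 | 10.4% | 10.7% | 25.8% |

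**Step 4. Translate into the plan's success rule.** Success is non-rejection, so the chance of success is 1 minus power. With 114 per group and a true difference of 1.0 week, the study meets its criterion with probability 1 − 0.795 = 20.5% and fails it with probability 79.5%. With a true difference of 0.5 week it meets the criterion with probability 1 − 0.285 = 71.5%. With 400 analysed per group, that last figure is 1 − 0.744 = 25.6%.

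**The case against.** The strongest reply is that the calculation is right and only one phrase is wrong. This stands: every number in the section reproduces at 1.0 week. The sentence calling this the smallest effect worth detecting also treats 1.0 week as a single target value, so an attentive reader can recover the intended meaning. It does not make the power sentence correct. It makes the paragraph inconsistent, since a smallest effect of interest is a floor and the sentence before it gives a ceiling.

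A second reply is that up to 400 per group may be recruited, which raises power at 0.5 week to 74.4%. That also stands, and the corrected text should say so. But 400 is a ceiling, it applies before the exclusions listed under Statistical Analysis Plan, and the 80% is tied explicitly to 114. Even with 400 analysed per group, 80% power begins at about 0.53 week, so it still does not cover all differences below 1.0 week.

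A third reply is that the 1.0 week is a garbled margin. A non-inferiority calculation with margin 1.0 week, one-sided alpha 0.025 and true difference zero does give 115 per group. The documents do not support that reading: the hypotheses are a two-sided test of difference, the power is for a significant result, and no margin is defined.

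A reader might also infer that power collapses just below 1.0 week. It does not. The decline is gradual, from 79.5% at 1.0 week to 70.7% at 0.9, and is severe only by about 0.5 week.

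**Conclusion.** The power sentence is wrong as written and should be corrected. With 114 per group, 80% power belongs to a true difference of about 1.0 week or more. At 0.8 week it is 60.5% and at 0.5 week 28.5%. These figures rest on the plan's own inputs: standard deviation 2.7 weeks in both groups, all 114 per group analysed, and an unadjusted two-sample comparison at two-sided 0.05.

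Two stronger conclusions might be drawn, and neither follows from this point. One is that the sample size is miscalculated or too small; it is sound for detecting a 1.0-week difference, and so is the stated precision. The other is that the reversed wording is what makes a null result over-reassuring. That comes mainly from treating non-rejection as success, which would remain after the wording is corrected and is a separate matter.

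**What to change.** Replace the power statement and its condition with text along these lines:

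> With 114 per group, a standard deviation of 2.7 weeks and two-sided alpha 0.05, the study has 80% power to detect a true mean difference of 1.0 week. Power at a true difference of 0.5 week is about 28.5% (about 74% if 400 per group are analysed). Because success is defined as non-rejection of the null hypothesis, the 80% is the probability that the study does not meet its success criterion when the true difference is 1.0 week.

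The cost is two or three sentences of protocol text. The 114, the 80%, the 0.70-week precision and the test all stay as they are. The one drawback for the sponsor is that the stated power for small differences looks less favourable. Any change to the success rule, or the introduction of a margin, should be considered separately and would need its own power statement.

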- 10. Were you seriously injured during your "study pregnancy", e.g., had a car accident, work injury, home accident, assault, etc.?
 - Yes

TCH-011 Clinical Study Protocol

Doc ID: TECXXXX

Revision #: 1.0

Page: 10 of 25

No

Yes = not eligible

- 11. Do you have a history of preterm birth (delivery at gestational age under 37 weeks) with any of your previous pregnancies (before the "study pregnancy")?
 - Yes
 - No

Yes = not eligible

- 12. Do you have a history of congenital malformations or birth defects in any of your previous pregnancies (before the "study pregnancy")?
 - Yes
 - No

Yes = not eligible

Eligibility messages:

Not eligible message: Message presented to subjects if they do **not meet** the eligibility criteria as identified during the screening questionnaire:

Thank you for your interest in the study on migraine treatments during pregnancy. However, the information you provided indicates that you do not meet the study eligibility requirements, and therefore cannot participate in this survey study.

Eligible message: Message presented to subjects upon the completion of the screening questionnaire, if they **meet** the eligibility criteria as identified during the screening questionnaire:

Thank you for your interest in the study on migraine treatments during pregnancy.

The information you provided indicates that you are eligible to participate in this survey study.

You will now be directed to an electronic informed consent form. Please read the consent form carefully. If you consent, please provide your details and electronic signature at the bottom of the consent form.

Once signed, you will be directed to the survey study questionnaire.

The questionnaire contains 52 questions. It should take approximately 30-40 min to complete the questionnaire.

In order to make it easier and faster to answer the survey questions, we recommend you prepare documents you received upon hospital discharge following delivery of your "study pregnancy", prior to answering the questionnaire.

Please select your referral clinic:

QMS document

TCH-011 Clinical Study Protocol

Doc ID: TECXXXX
Revision #: 1.0

Page: 11 of 25

- 1. Clinic A
- 2. Clinic B
- 3. Clinic C
- 4. Clinic D
- 5. Clinic E
- 6. Other

Single choice

Present the matching ICF, based on participant's clinic

QMS document

TCH-011 Clinical Study Protocol

Doc ID: TECXXXX

Revision #: 1.0

Page: 12 of 25

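### Controls come through clinics and Nerivio users do not, so the 80% power and ±0.70-week precision are too optimistic if clinics differ; how much depends on figures the plan does not give

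*Combined protocol and SAP*

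**What the plan says.** The two groups are recruited by different routes. Under Study Design and Recruitment, Nerivio users are invited individually, by in-app notification or email to the device's user base. For controls the same section says: "Control group participants will be referred to the study by site co-investigators, who are US licensed healthcare providers seeing women with headache disorders" and/or women before or during pregnancy. The opening summary names headache specialists and OBGYNs as the referrers.

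Appendix 1 ends with "Please select your referral clinic", a single-choice list of Clinic A to Clinic E plus Other. The answer determines which consent form is shown. The item belongs to the message for every eligible woman, not only controls. The closing page of Appendix 2 makes payment to any participant follow verification with the clinic.

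Planned Sample Size states: "With the proposed sample size of 114 for each group, the study will have power of 80% to yield a statistically significant result". It adds: "This computation assumes that the mean difference is less than 1.0 week, and the common within-group standard deviation is 2.7". On precision it says: "On average, a study of this design would enable us to report the mean difference with a precision (95% confidence level) of plus/minus 0.70 weeks", and then that "up to 400 participants will be recruited per group". Statistical Hypothesis compares two mean gestational ages: "The criterion for significance has been set at 0.05. The test is 2-tailed". Success is failure to reject equality. No test or model is named. The Statistical Analysis Plan section lists only exclusions from analysis. Nothing in these sections mentions a clinic effect, an ICC, a design effect or a robust variance.

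**The concern.** Women referred by the same practice may resemble one another. A headache practice and an obstetric practice can draw different patients, and obstetric practices can differ in the timing of delivery. If clinics differ in mean gestational age, the control mean carries between-clinic variation that a calculation for independent women leaves out. To the extent that Nerivio users do not belong to the same clinics, this variation does not cancel in the difference between groups.

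What is at stake is the interval. In a pregnancy-safety study, an interval that is too narrow can appear to exclude a 1.0-week difference when the data do not. A chance mix of a few clinics could also be reported as a difference. Recruiting more women from the same few clinics makes the understatement proportionally larger.

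**Working it through.** **Inputs from the plan:** 114 per group, SD 2.7, difference 1.0 week, two-sided 0.05, ceiling 400 per group. **Assumed, because the documents give no figure:** k equal-sized control clinics (5, matching the listed slots; 10 and 20 as a range), ICC 0.01 to 0.05, Nerivio users independent, total SD kept at 2.7.

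**1. The plan's own figures.** SE = 2.7 × √(2/114) = 0.358. Half-width = 1.96 × 0.358 = 0.70 weeks. Power = Φ(1.0/0.358 − 1.96) = 79.8%. Both match the plan, with a design effect of 1 in both groups.

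**2. Clustered controls, 114 per group, 5 clinics.** Control design effect DE = 1 + (114/5 − 1) × ICC = 1 + 21.8 × ICC. SE = 2.7 × √((1 + DE)/114). Half-width = 1.96 × SE. Power = Φ(1.0/SE − 1.96). Type I error of a two-sample test that ignores clinic = 2 × (1 − Φ(0.701/SE)).

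| ICC | DE | SE | Half-width | Power | Type I error, clinic ignored |
|---|---|---|---|---|---|
| 0 | 1.00 | 0.358 | ±0.70 | 80% | 5.0% |
| 0.01 | 1.22 | 0.377 | ±0.74 | 76% | 6.3% |
| 0.02 | 1.44 | 0.395 | ±0.77 | 72% | 7.6% |
| 0.05 | 2.09 | 0.444 | ±0.87 | 61% | 11.5% |

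**3. Few clinics, few degrees of freedom.** With Satterthwaite degrees of freedom (k − 1 = 4 for the control variance, 113 for the Nerivio variance), the half-width at the true variances is ±0.76, ±0.81, ±0.87 and ±1.01 for ICC 0, 0.01, 0.02 and 0.05. The average width in simulated trials, where the variances are estimated, is slightly smaller: about ±0.75, ±0.80, ±0.85 and ±0.98.

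**4. More clinics, 114 per group (normal approximation).** With 10 clinics: ±0.74 and 76% power at ICC 0.02, ±0.79 and 70% at ICC 0.05. With 20 clinics, ICC 0.01 to 0.05: ±0.71 to ±0.74, power 79% to 75%.

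**5. The ceiling of 400 per group, 5 clinics.** DE = 1 + 79 × ICC = 1.79, 2.58 and 4.95 for ICC 0.01, 0.02 and 0.05. An interval that ignores clinic reads 1.96 × 2.7 × √(2/400) = ±0.37. The true half-width is ±0.44, ±0.50 and ±0.65 by normal approximation, so the stated ±0.70 is still met. With the degrees of freedom of step 3 it is ±0.81 at ICC 0.05.

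**6. Effect on the plan's success rule.** Take a true 1.0-week difference, 114 per group, 5 clinics and ICC 0.05. A test that ignores clinic rejects with probability Φ((1.0 − 0.701)/0.444) = 75%, so success is declared wrongly about 25% of the time. A clustered test with small-sample degrees of freedom rejects about 51 to 52% of the time, so wrongful success rises to about 48 to 49%.

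**The case against.** The case on the other side is substantial.

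- **Nesting.** A reader might infer that clinic lies wholly inside the control group. The documents do not establish this. Every eligible woman sees the clinic item, and nothing says whether Nerivio users choose Other or a listed clinic. If some choose a listed clinic, clinic partly crosses the groups and some between-clinic variation cancels.
- **Number of clinics.** A reader might infer five. Clinics A to E are unnamed placeholders with Other beside them, and no number of sites is stated.
- **ICC.** None is given. ICC 0.05 means a between-clinic SD of 2.7 × √0.05 = 0.60 weeks. About 24% of clinic pairs would then have true means more than 1.0 week apart: 2 × (1 − Φ(1/(0.60 × √2))). At ICC 0.01 the SD is 0.27 weeks and the share about 1%. Nor do the documents say that the referring clinic managed the delivery.
- **No named test.** The error rates in the working are those of a two-sample test that the plan never names. Independence is inferred from the sizing and from the silence of the analysis section.
- **Direction.** A reader might infer that ignoring clinics makes success easier. Under the plan's rule the reverse holds: excess false rejections count against success, and wider error bars make non-rejection easier.

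The first four points limit how large the problem can be said to be. The fifth means that clustering should not be added while success still rests on non-rejection. None of them changes the fact that ±0.70 weeks and 80% power assume no between-clinic variation, without saying so, in a design that refers all controls through clinics.

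**Conclusion.** The concern holds conditionally: if clinics differ in mean gestational age, the stated power and precision are too optimistic and an unclustered interval is too narrow. The size rests on an assumed ICC and clinic count. It ranges from negligible (20 clinics, or an ICC near 0.01, at 114 per group) to material: five clinics and ICC 0.05 leave 61% power and a half-width of ±0.87, or about ±0.98 with small-cluster degrees of freedom, close to the plan's smallest important difference.

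At 400 per group it would be wrong to say that the promised ±0.70 is lost. By normal approximation it is met over this ICC range. What fails there is the reported interval, which would read ±0.37 when the true one is ±0.44 to ±0.65. The documents do not support a claim that the study's real type I error is any particular value.

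This is a point about variance. Allowing for clinic does not remove bias from recruiting the two groups by different routes.

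**What to change.** 1. In the Statistical Analysis Plan, report the difference in mean gestational age with a 95% interval that allows for clustering by referral clinic among referred women, using small-sample degrees of freedom. Judge that interval against the plan's own 1.0-week difference instead of by non-rejection.
2. Use the Appendix 1 clinic item as the cluster variable, and add a name field for Other. State how Nerivio users answer it: each is her own cluster unless she selects a study clinic, in which case that clinic is shared across the groups.
3. In Planned Sample Size, state that 80% power and ±0.70 weeks assume no between-clinic variation. Give the expected number of clinics and the figures over an ICC range.
4. Do not require the clustered model for rare binary secondary endpoints such as stillbirth, where few clusters make it unstable.

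The cost is plan wording and one form field, with no extra procedures. Intervals widen slightly even if the ICC is zero (about ±0.75 instead of ±0.70 with five clinics), and degrees of freedom are few. Judging by the interval is also more demanding. With no true difference and 114 per group, the chance that the whole interval lies within ±1.0 week is 2 × Φ((1.0 − 0.701)/0.358) − 1 = 60% without clustering, and 2 × Φ((1.0 − 0.871)/0.444) − 1 = 23% at ICC 0.05 with five clinics (normal approximation). The sponsor should therefore settle the enrolment target and the number of clinics together.
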